5 TRIAL SETTING

The trial will initially run as a single center study in order to assess reproducibility and feasibility across different sites. The main host center will be The Royal Wolverhampton NHS Trust.

6 PARTICIPANT ELIGIBILITY CRITERIA

6.1 Inclusion criteria

- Participant is willing and able to give informed consent for participation in the study.
- Male or Female, aged 18+ years.
- Diagnosed with histologically or radiologically diagnosed colorectal adenocarcinoma.
- Anaemic at point of diagnosis of colorectal adenocarcinoma (Defined as haemoglobin 10g/L below WHO criteria: 120g/L for males and 110g/L for females, to account for a 10% fluctuation in Hb)
- Undergoing surgery for colorectal cancer with curative intent.
- Date of planned surgery is \geq 14 days from date of planned initiation of recruitment.
- Able (in the investigators opinion) and willing to comply with all study requirements.
- Willing to allow his or her General Practitioner and consultant, if appropriate, to be notified of participation in the study.

6.2 Exclusion criteria

- Patients with mental health issues or learning disabilities resulting in their inability to consent to the study

- Patients who do not have a histological diagnosis of colorectal adenocarcinoma
- Female participants who are pregnant, lactating or planning a pregnancy during the course of the study.
- Patients with evidence of iron overload or disturbances in utilisation of iron as stated in the product SPC.
- Previous gastric, small bowel or colorectal surgery (where ≥50% of stomach or terminal ileum has been resected)
- Chemotherapeutic treatment within the last 4 weeks.
- Known previous anaemia not attributable to colorectal carcinoma (i.e. anaemia in patients with well established, inflammatory disorders)
- Known haematological disease.
- Features necessitating urgent surgery (e.g. obstructive symptoms).
- Previous allergy to intravenous or oral iron or related iron products.
- Patients who are unable to consent.
- Any other significant disease or disorder which, in the opinion of the Investigator, may either put the participants at risk because of participation in the study, or may influence the result of the study, or the participant's ability to participate in the study.
- Participants who have participated in another research study involving an investigational product in the past 12 weeks
- Confirmed liver or lung metastases

7 TRIAL PROCEDURES

7.1 Recruitment

Identification of suitable subjects will occur via the surgical outpatient clinics and the colorectal cancer MDT meetings. This will be conducted by the clinical team, nurse specialists, research nurses and the clinical research fellow. Recruitment will take place following explanation of the cancer diagnosis and treatment plan by the clinical team. The patient will be aware of the diagnosis and the plan for surgery at the point of attendance. The patient will also be aware that they are anaemic.

Initially the patient will be approached by a member of the clinical team. Following this the research team will explain the trial to the patient and provide them with a patient information

sheet. Alternatively, the patient may be sent the information sheet in the post by any of the relevant clinical or research teams. Following explanation of the trial the patient will be given adequate time to deliberate the information and ask questions. If the patient wishes to join the trial at that point, they will be invited to sign the informed consent form. Patients will be offered participation in the optional sample sub-study. After valid informed consent is given, the study procedures will commence at this visit and baseline assessments will be undertaken. The additional visits for intervention and follow up will then be planned.

7.1.1 Participant identification

All patients who attend the surgical outpatient clinic for a two-week wait appointment or who are found to have an abnormal lesion on lower gastrointestinal endoscopy or who are discussed at the colorectal cancer MDT will be screened for eligibility. As part of standard clinical practice all patients will have their haemoglobin level checked to determine if they are anaemic. Patients who are found to have an abnormal lesion will be discussed at the weekly colorectal cancer MDT meeting. Patients who are anaemic and who are diagnosed to have adenocarcinoma within the lower gastrointestinal tract will be identified at the MDT meeting. The research team will liaise with the colorectal nurse specialists who attend the MDT meetings. After the MDT meeting a patient will be called to clinic to inform them of the diagnosis, outcome and any plan for surgical management. In certain cases this clinic visit may be replaced by a phone call from a colorectal nurse specialists.

Once the patients have been informed of their diagnosis and the management plan, a member of the clinical or research team will introduce the trial to the patient and subsequently the first discussion with the research team will take place. Eligibility will be confirmed by a medical practitioner.

7.1.2 Screening

Screening will be undertaken using the results of existing investigations carried out as part of the normal colorectal cancer pathway as stated above. If a potentially eligible patient is identified by the screening process but is found to not have had a recent haemoglobin level checked within one month, then the research team will identify and refer this patient to the clinical team. The patient can then be advised to have their blood retested at their GP practice, or be provided with a blood form to undergo the testing in the hospital setting. This blood testing is part of standard pre-treatment clinical practice.

7.1.3 Payment

No payments or incentives will be given to study participants

7.2 Consent

A named member of the clinical or research team, who are on the study's delegation log, will take consent from the participant once they have ascertained that the patient fits the eligibility and inclusion criteria.

It will be clearly stated that the participant is free to withdraw from the study or the optional sample sub-study at any time for any reason without prejudice to future care, and with no obligation to give the reason for withdrawal. The participant will be allowed as much time as wished to consider the information, and the opportunity to question the Investigator, their GP or other independent parties to decide whether they will participate in the study. Written informed consent will then be obtained by means of participant dated signature and dated signature of the person who presented and obtained the informed consent. The person who obtained the consent will have been authorised to do so by the Chief/Principal Investigator. A copy of the signed informed consent will be given to the participants. The original signed form will be retained at the study site. A copy of the signed informed consent will be placed in the participant's medical notes.

7.3 The Randomisation scheme

Randomisation will be undertaken via an online platform in a 1:1 fashion to either the control group (standard care) or the intervention group (postoperative ferric maltol). The study will be an open label design and participants will be informed of their group allocation after their operation. Randomisation alerts with allocation details will be emailed to the CI, research fellow, research nurses and the pharmacy team.

7.4 Blinding

Patient and investigator will not be blinded to the study treatment allocation due to the change in stool colour with oral iron intake. It is not possible to simulate this change with a placebo “dummy” drug for the control group.

7.5 Baseline data

Following the consent process the following baseline data will be recorded

- *Demographics*

Date of birth, gender, race, smoking status, alcohol intake, height and weight

- *Medical History*

History of any disease or surgical interventions including the relevant dates

- *Concomitant medication & drug allergies*

Dose, route, start date (and end date of medication if medication was stopped within the six weeks prior to recruitment)

Start and end date of any iron supplements

Compliance to medication

- *Laboratory tests*

Haematologic markers: Full blood count, iron, ferritin, transferrin, transferrin saturation, erythropoietin

Inflammatory markers: C-reactive protein levels

Female participants of child-bearing age will undergo a urine pregnancy test, as is routine with patients undergoing surgery

- *Optional samples for sub-study*

Urine, stool, saliva and sweat samples may be taken for analyses

- *Questionnaires*

Quality of life score (using SF36, EQ-5D and FACT-An questionnaires)

- Grip strength may be recorded

7.7 Trial assessments

Following the consent process and baseline data collection the patient will attend for their preoperative iron infusion, as is routine care. They will then undergo the following trial assessments:

Day of Surgery (on the morning of their operation.):

- A brief interview will take place at the surgical pre-operative assessment ward to ascertain if the patient had any questions or if they experienced any side-effects in the intervening time. Any pre-operative blood transfusion will be noted. Information will be documented in the CRF.
- Blood will be drawn for the following tests: Full blood count, C reactive protein, iron, ferritin, transferrin, transferrin saturation, and erythropoietin.
- Optional sub-study urine, stool, saliva and sweat samples may be taken for analyses
- Grip strength may be recorded

- The participant will be requested to complete Quality of Life (QoL) questionnaires SF36, EQ-5D and FACT- An questionnaires.

Postoperatively they will be randomised to either the intervention group or the control group and the following assessments will be undertaken

Day 2 postoperatively.

- Information regarding the peri-operative period, intraoperative blood loss and any transfusion requirements will be documented in the CRF.
- Blood will be drawn for the following tests: Full blood count, erythropoietin, C-reactive protein, iron, ferritin, transferrin, transferrin saturation.
- Optional sub-study urine, stool, saliva and sweat samples may be taken for analyses
- Grip strength may be recorded
- At this point the Haemoglobin will be used to confirm postoperative anaemia (Hb <130g/L men, <120g/L women) allowing patients to commence their allocated treatment pathway according to randomisation.

Day 3 postoperatively.

- Blood will be drawn for the following tests: Full blood count, erythropoietin, C reactive protein, iron, ferritin, transferrin, transferrin saturation.
- Optional sub-study urine, stool, saliva and sweat samples may be taken for analyses
- Grip strength may be recorded

Day 5 postoperatively (if remains an inpatient).

- Blood will be drawn for the following tests: Full blood count.
- Optional sub-study urine, stool, saliva and sweat samples may be taken for analyses
- Grip strength may be recorded

Entry into postoperative treatment pathway

If a patient is found to be not anaemic on day 2 postoperatively (Hb \geq 130g/L men, \geq 120g/L women) they will complete screening and remain in the study but will not enter their allocated treatment pathway (i.e ferric maltol or standard care). If they remain anaemic on day 3 or day 5 blood tests they will, at this stage, enter their allocated treatment pathway. If patients have a normal haemoglobin on days 2, 3 or 5 they will be withdrawn from the study.

Outpatient Follow Up

Finally, after discharge the patient will be seen in their first outpatient clinic at 8-12 weeks postoperatively. Where follow up occurs earlier, for example, due to the clinician's normal practice or due to a complication, then the usual 8-12 week outpatient visit will still be used.

At this visit the following assessments will be undertaken

- Information regarding postoperative complications, the length of hospital stay and readmissions to hospital will be documented in the CRF
- Any postoperative transfusion requirements will be documented in the CRF.
- Blood will be drawn for the following tests: Full blood count, erythropoietin, C-reactive protein, iron, ferritin, transferrin, transferrin saturation
- Optional sub-study urine, stool, saliva and sweat samples may be taken for analyses
- Grip strength may be recorded
- The participant will be requested to complete Quality of Life questionnaires: SF36, EQ-5D and FACT- An questionnaires.

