The participant is next reviewed when they are admitted on the morning of the operation.

Blood tests and the quality of life questionnaires will be repeated.

Preoperatively patients will undergo randomisation to one of the two study arms. After operation the participants haemoglobin will be checked on day 2 of their recovery. If, at this point, postoperative anaemia is confirmed they will enter into their study arm. The intervention group will commence a course of oral ferric maltol provided oral intake has recommenced and the control group will receive standard care. All patients will have blood tests checked again at day 3 and day 5 postoperatively if they remain as an inpatient. If they are found to be anaemic on either of these two blood tests they will, at this stage, enter their allocated treatment pathway. If a patient shows no evidence of anaemia on either day 2, 3 or 5 blood tests they will be withdrawn from the study. If the patients have consented to the optional sample sub-study, the patients may be asked to give other samples of faeces, urine, saliva or sweat at days 2, 3 or 5 along with the blood tests. Patients will continue treatment according to their randomisation allocation until 12 weeks after the operation, at which point the patient attends a routine surgical outpatient follow-up clinic. During the outpatient visit the participants will undergo their final blood and optional sample sub-study testing (if consented) as well as questionnaire completion.

The participants may only be required to attend the hospital for one extra visit to consent and where possible this will be arranged to coincide with existing appointments. The study is designed such that all other procedures are carried out when the participant attends for their routine visits as per the normal clinical pathway.

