7.8 Withdrawal criteria

There will be intention-to-treat analyses carried out. Analysis of all participants who have been randomised will be undertaken regardless of withdrawal. The reason for withdrawal will

be recorded in the CRF. Each participant has the right to withdraw study at any time. A participant will be withdrawn from the study if any of the following occurs:

- Absence of anaemia on postoperative days 2, 3 and 5.
- Pregnancy
- Ineligibility (either arising during the study or retrospective having been inadvertently overlooked at screening)
- Significant protocol deviation as defined by the CI
- An adverse event which requires discontinuation of the study medication or results in inability to continue to comply with study procedures
- Disease progression which requires discontinuation of the study medication or results in inability to continue to comply with study procedures
- Patients who do not undergo an operation as a result of a change in fitness for surgery will be excluded.
- Consent withdrawn.
- Lost to follow up

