8.5 Dosage schedules

Participants in the intervention arm will take one 30mg capsule twice daily, morning and evening, on an empty stomach. Treatment will commence as soon as postoperative anaemia is confirmed on day 2, 3 or 5 blood tests provided oral intake has been resumed and will continue until the first routine outpatient visit. If a dose is missed the subject will be allowed to take their missed dose within 6 hours of the correct time. If there is any interruption to treatment, for

example due to vomiting or illness, the patient will be asked to recommence treatment as soon as they are deemed safe to do so by a medical practitioner.

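### Three wordings of the rule for withdrawing non-anaemic patients conflict: read literally, section 7.7 withdraws patients already on their pathway, and section 7.8 misses never-anaemic patients discharged early

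*Combined protocol and SAP*

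**What the plan says.** All of the wording below is current text; Appendix 2 (section 16.2) records no amendments.

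- **Section 4 (Trial design).** Randomisation is before surgery, and a patient enters the allocated arm once a postoperative test confirms anaemia. On re-testing: "All patients will have blood tests checked again at day 3 and day 5 postoperatively if they remain as an inpatient". On withdrawal: "If a patient shows no evidence of anaemia on either day 2, 3 or 5 blood tests they will be withdrawn from the study". On duration: "Patients will continue treatment according to their randomisation allocation until 12 weeks after the operation".
- **Section 7.7 (Trial assessments, entry into the pathway).** A patient who is not anaemic on day 2 does not start the pathway, but "they will complete screening and remain in the study". Then: "If they remain anaemic on day 3 or day 5 blood tests they will, at this stage, enter their allocated treatment pathway". The paragraph ends: "If patients have a normal haemoglobin on days 2, 3 or 5 they will be withdrawn from the study". The visit list in the same section makes only the day 5 test conditional on still being an inpatient; day 3 carries no condition.
- **Section 7.8 (Withdrawal criteria).** The first bullet is "Absence of anaemia on postoperative days 2, 3 and 5".
- **Section 8.5 (Dosage schedules).** Once started, treatment "will continue until the first routine outpatient visit".

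Section 10.3.2 counts withdrawal, compliance and retention among the primary feasibility measures.

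**The concern.** The three sentences use different logic. Section 4 reads as never anaemic, section 7.7 as normal on any one day, and section 7.8 as normal on all three days. A site following 7.7 to the letter would withdraw a patient who started ferric maltol on day 2 and had a normal haemoglobin on day 3 or day 5. A site following 7.8 to the letter would have no withdrawal criterion for a patient with normal results who goes home before day 5.

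The rule acts on patients who are already randomised. It decides who stops treatment and follow-up, and who is counted as withdrawn or retained. Those counts are part of what the study sets out to measure and will inform the planning of a definitive trial.

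**Working it through.** The plan gives no figure to reproduce. The check lists every possible sequence of results on days 2, 3 and 5 and applies each wording to it. A = anaemic, N = normal, - = not tested because discharged.

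**Number of patterns**
- If days 3 and 5 are both inpatient-only (section 4): 2 with one test + 4 with two + 8 with three = 14.
- If only day 5 is inpatient-only (section 7.7 visit list): 4 + 8 = 12. The patterns A-- and N-- drop out.

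**Applying each wording**

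| Group | Patterns | Section 4, read naturally | Section 7.7, last sentence read literally | Section 7.8, read literally |
|---|---|---|---|---|
| Never anaemic | N--, NN-, NNN | withdraw | withdraw | withdraw NNN only |
| On the pathway, then a normal re-test | AN-, AAN, ANA, ANN, NAN | keep | **withdraw** | keep |
| Normal first, then anaemic, no later normal result | NA-, NAA, NNA | keep | withdraw, against the paragraph's earlier sentences | keep |
| Anaemic on every test | A--, AA-, AAA | keep | keep | keep |

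Check: 3 + 5 + 3 + 3 = 14. Without N-- and A--: 2 + 5 + 3 + 2 = 12.

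**Section 7.7**
1. The last sentence, taken alone, withdraws every pattern containing an N: 3 + 5 + 3 = 11 of 14.
2. Three of these (NA-, NAA, NNA) are rescued by the earlier sentences of the same paragraph, which keep a day-2-normal patient in the study and allow late entry. For these patients the paragraph contradicts itself.
3. Five (AN-, AAN, ANA, ANN, NAN) are patients already on their pathway. NAN belongs here: the earlier sentences carry that patient to entry on day 3, but do not say what a normal day 5 result then means. The count is five under either assumption about day 3.
4. Such results can arise because section 4 re-tests all inpatients, including those already on treatment. Sections 4 and 8.5 keep these patients on treatment to the outpatient visit.

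**Section 7.8**
1. Only NNN meets a condition naming all three days.
2. NN- is missed under either assumption. N-- is also missed if day 3 is inpatient-only. The gap is therefore two patterns under section 4's schedule and one under 7.7's visit list.
3. No other 7.8 bullet clearly covers these patients. Postoperative anaemia is not an inclusion criterion in 6.1, so the ineligibility bullet does not plainly apply. The missing-data rule in 10.5 is a poor fit too, because a test that is not due after discharge is not lost data.

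**Scale of one case.** With 20 patients per arm (section 10.1), one reclassified patient moves an arm's retention by 1/20 = 5 percentage points. This is the effect per patient, not an estimate of how many patients are affected.

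**The case against.** The strongest reply is that the 7.7 sentence has been lifted out of its paragraph. That paragraph is about entry to the pathway, opens with patients who are normal on day 2, and says when they may enter late. In context, its last sentence disposes of those who never enter. Section 4 follows the same sequence, and its own rule already withdraws the never-anaemic patient who goes home early, so 7.8 is only a less complete restatement. The study is also a 40-patient feasibility trial with descriptive analysis (10.2) and no a priori feasibility criteria (3.3.1). All randomised participants are analysed regardless of withdrawal, and reasons for withdrawal are recorded (7.8), so withdrawals for absence of anaemia can be separated from other attrition.

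Most of this stands. The intent can be inferred, and sensible staff would probably follow it. A reader might go further and infer that the early-discharge patient has no governing rule anywhere. The documents do not support that, because section 4 supplies one. A reader might also infer that withdrawn patients drop out of the analysis set; 7.8 says otherwise.

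What the reply does not remove is that 7.7 states an action on randomised patients that sections 4 and 8.5 contradict, and that the formal list of criteria in 7.8 is incomplete. Analysing all randomised patients does not restore treatment or follow-up that was stopped, and the patient still counts as withdrawn.

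**Conclusion.** The point holds as a minor wording defect. The three statements of the rule conflict. Section 7.7, read literally, withdraws five patterns of patient already on the allocated pathway and contradicts its own treatment of a normal day 2 result. Section 7.8, read literally, misses one or two never-anaemic patterns, depending on whether the day 3 test is inpatient-only.

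The effect is confined to who stops treatment and follow-up and to the withdrawal and retention counts. The pattern counts are logical cases that need not be equally likely, and no rate can be derived from the documents. It would be tempting to call this a design error, or to predict that treated patients will be withdrawn in numbers. Neither is supported: the intended rule, withdrawing only patients never found anaemic, can be recovered from section 4 and from the rest of the 7.7 paragraph. The conclusion rests on a literal reading of 7.7 and 7.8 and a natural reading of section 4.

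**What to change.** Use one criterion in sections 4 and 7.7 and as the first bullet of 7.8, as the only withdrawal rule based on absence of anaemia:

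*No anaemia on any haemoglobin test taken on postoperative day 2, 3 or 5 (tests done while an inpatient).*

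In section 7.7 only, add:

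*Once a patient has entered the allocated pathway, a later normal haemoglobin is not a reason for withdrawal; treatment and follow-up continue to the outpatient visit as in sections 4 and 8.5.*

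The second sentence is not a withdrawal criterion, so it does not belong in the 7.8 list. Referring to the outpatient visit avoids a new clash between the 12 weeks in section 4 and the 8-12 weeks in section 7.7. With this text, N--, NN- and NNN are withdrawn and every other pattern stays in.

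The parenthesis follows section 4 in treating day 3 as inpatient-only. If the day 3 test is meant for everyone, section 4 should say so and the parenthesis should apply to day 5 alone.

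The cost is a text change in three places, with no extra visits, tests or patients. It goes through the amendment route in sections 13.7 and 16.2.
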